6.14.2.3 ADHD-RS-5 Hyperactivity/Impulsivity and Inattention Subscales

The change from baseline to EOS in ADHD-RS-5 Inattention and the change from baseline to Week 8 (EOS) in Hyperactivity/Impulsivity subscales will be analyzed using ANCOVA model with fixed effects for treatment, age group and baseline as a covariate. Each of the treatment groups (SPN-812 ER 200 mg and 400 mg) will be compared with the Placebo. The p-values, LS means of treatment groups, differences between the LS means and placebo will be presented. The summary of this analysis will be presented in Table 14.2.2.3.

6.14.2.4 Conners 3rd edition (Conners 3) – self (ages 8-11)

The Conners 3-PS analysis from Section 6.14.1.2 will be repeated here. The summary of this analysis will be presented in 14.2.2.4.

6.14.2.5 Categorical Analysis of CGI-I

Categorical analysis will be performed using Pearson's Chi-square test by dichotomizing the CGI-I score as 'Improved' if the score is 'very much improved' or 'much improved' and 'Not Improved', otherwise, and will be presented for each visit in Table 14.2.2.5.

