3.5 Sample Size and Power Considerations

Seventy-two subjects per treatment group in the ITT population will yield 90% power at a significance level of 0.05 (two-sided) using a two-sample t-test with equal allocation to the treatment

groups. This assumes an effect size of 0.547, observed in the comparison of SPN-812 200 mg and placebo in the SPN-812 Phase IIb study (based on the CFB to endpoint in the ADHD-RS-IV total score). A total of 300 subjects (100 subjects in each of the three treatment groups) will be randomized to account for an anticipated 27.9% of randomized subjects not completing the study.

4 Definitions and Derivations

1. Baseline: Unless specified otherwise, baseline is defined as the non-missing value collected most recent to and before the time of the very first dose of the SM.
2. The study day (DY) is calculated as Visit date minus Reference date + 1 day if the visit date occurs on or after the reference date or Visit date minus Reference date if the visit date occurs before the Reference date, where the Reference date is defined as the first dose date (DY=1)
3. The change from baseline at a given Visit = observed value at that Visit minus observed value at baseline
4. ADHD-RS-5 total score =sum of scores for the 18 behaviors
5. ADHD-RS-5 Inattention subscale score = sum of scores for the first 9 behaviors
6. ADHD-RS-5 Hyperactivity/Impulsivity Subscale score = sum of scores for the last 9 behaviors
7. Conners 3-Parent Reported score: Composite T-score calculated by averaging over the 6 domains
8. Conners 3-Parent Reported score: T-score for individual domain: inattention, hyperactivity/impulsivity, aggression, executive functioning, learning problems, and relationships
9. Conners 3-Self Reported score domains: Composite T-score over the 5 domains
10. Conners 3-Self Reported score domains: inattention, hyperactivity/impulsivity, aggression, learning problems, and relationships
11. WFIRS-P score=average of all 50 items
12. WFIRS-P subscale scores: average of items of following 6 subdomains: Family, School (learning and behavior), Life Skills, Child's Self-Concept, Social Activities, and Risky Activities
13. PSI-4-SF: score=sum of all 36 items
14. PSI-4-SF: subscale scores: sum of items of following 3 subdomains: parental distress (PD), parent-child dysfunctional interaction (P-CDI), and difficult child (DC)

5 Study Variables

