5.2 Secondary Efficacy Variables

5.2.1 Clinical Global Impression-Improvement

The CGI scale was developed to provide a brief, stand-alone assessment of the clinician's view of a subject's global functioning prior to and after administration of a SM ([Guy 1976](#)). The Clinical Global Impression – Severity of Illness (CGI-S) is a single item clinician rating of clinician's assessment of the severity of the ADHD symptoms in relation to the clinician's total experience with patients with ADHD. The Clinical Global Impression – Improvement Scale (CGI-I) is an assessment of how much the patient's illness has improved or worsened relative to a baseline state at the beginning of treatment. Both CGI-S and CGI-I are rated on a 7-point scale of 1 to 7 with 7 being "extremely ill" or "very much worse", respectively. Successful therapy is indicated by a lower overall score in subsequent testing.

CGI-I, relative to the condition at baseline, will be evaluated by the Investigator at each post-baseline visit on a 7-point scale with 1=Very much improved, 2=Much improved, 3=Minimally improved, 4=No change, 5=Minimally worse, 6=Much worse, and 7=Very much worse.

5.2.2 Conners 3

The Conners 3rd Edition™ (Conners 3) is a focused diagnostic tool for assessment of ADHD and associated learning, behavior, and emotional problems in children ages 6 to 18 years ([Sparrow, 2010](#)). The scale is based on the solid findings and key elements of its predecessor, the Conners Rating Scales-Revised (CRS-R™), but offers a more refined assessment of ADHD and comorbid

disorders (e.g., oppositional defiant disorder and conduct disorder). The Conners 3 instrument includes items related to inattention, hyperactivity, and impulsivity, as well as assessments of executive functioning, learning problems, and relationships. Like previous versions, the Conners 3 combines teacher, parent, and student reports to provide a particularly detailed and comprehensive evaluation of student behavior as observed in different settings. Teacher, parent, and self-report (for 8-18y.o.) rating scales are all available in long and short versions. The short forms of Parent, Teacher, and Self Reports of Conners 3 are comprised (respectively) of 45, 41, and 41 items. All Conners 3 scale versions are scored on a 4-point scale (0-3), where a higher score indicates more severe symptom presentation.

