6.1 General Principles

All statistical analysis will be performed using SAS version 9.2 or higher by [REDACTED], which is the designated CRO. [REDACTED] will be responsible for creating TLF reports by SAS programming and delivering the reports as well as the programs to Supernus at the completion of the study.

All tabulations of analysis results will include summaries for the following three treatments: SPN-812 ER 400 mg, SPN-812 ER 200 mg, and placebo.

Where appropriate, variables will be summarized descriptively (frequency count and percent for categorical variables, and number of subjects (n), mean, standard deviation (SD), median, minimum, and maximum for continuous variables).

Means, least-squares (LS) means and medians will be presented to 1 more decimal place than the recorded data. Standard deviations and standard errors will be presented to two (2) more decimal places than the recorded data. Minimum and maximum values will be presented using the same number of decimal places as the recorded data. Confidence intervals will be presented using the same number of decimal places as the parameters (e.g., mean). Percentages will be presented to one (1) decimal place. P-values will use four decimal places.

Categorical variables will be analyzed using categorical response methods such as Pearson's Chi-square test. If expected frequencies are too small for asymptotic assumptions, exact testing techniques will be used.

The data summaries will be accompanied by individual subject data listings, as specified in Sections 16.2 and 16.4 of ICH Guidance E3, sorted by unique subject identifier. All data available from the electronic case report forms (eCRFs) will be listed. Unscheduled measurements will be excluded from the descriptive statistics and statistical analysis but will be included in listings. The

“EARLY_TERMINATION VISIT” for early discontinued subjects will be assumed to correspond to Visit 10 for statistical summaries but displayed as is in listings.

Derived analysis datasets will be produced from the SDTM data. Specifications for derived datasets will be developed. Analysis datasets to be created will include ADQS (Questionnaire analysis dataset), ADEFF1 and ADEFF2 (efficacy analysis dataset2), ADSL (subject-level analysis dataset), ADAE (Adverse event analysis dataset) and other as appropriate.

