6.14 Analysis of Secondary Endpoints

All secondary analyses are based on the ITT population with missing values imputed at week 8 (WK8) using multiple imputation (MI) assuming MAR using SEED=2460650. In case imputed values are below or above the range of the applicable scale, values will be imputed to respectively the minimum or maximum value of the scale. The following SAS code will be used MI.

```
PROC MI DATA=EFF NIMPUTE=100 SEED=2460650 OUT=MIOUT;  
  CLASS TREATMENT;  
  VAR TREATMENT BASELINE WK8(EOS);  
  FCS REG;  
RUN ;
```

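### Week 8 CGI-I is imputed as an unrounded continuous score, but the categorical CGI-I rule classifies only by whole categories, so fractional imputed scores can be wrongly classed as Not Improved

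*SAP*

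**What the plan says.** Section 5.2.1 defines CGI-I as a rating in seven whole categories, beginning "1=Very much improved, 2=Much improved, 3=Minimally improved, 4=No change" and ending at 7.

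Section 6.14 sets the missing-data rule: "All secondary analyses are based on the ITT population with missing values imputed at week 8 (WK8) using multiple imputation (MI) assuming MAR". The code shown there uses FCS REG with 100 imputations and no rounding option. The one correction described is truncation: "In case imputed values are below or above the range of the applicable scale, values will be imputed to respectively the minimum or maximum" of the scale.

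Section 6.14.2.5 stands under the additional secondary endpoints and specifies a Pearson chi-square test after "dichotomizing the CGI-I score as 'Improved' if the score is 'very much improved' or 'much improved' and 'Not Improved', otherwise". The result "will be presented for each visit in Table 14.2.2.5". The section gives no numeric cut-off, does not say whether observed or imputed data are used, and does not say how chi-square results from 100 datasets are to be combined.

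Two other places affect the size of the problem. Section 6.1 says that the early-termination visit "for early discontinued subjects will be assumed to correspond to Visit 10 for statistical summaries". Section 3.5 anticipates "27.9% of randomized subjects not completing the study".

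**The concern.** A regression imputation of a seven-category rating produces values that lie between categories. The responder rule recognises two categories and sends everything else to Not Improved. The two sections were each written sensibly but do not fit together: an imputed 1.6 carries neither qualifying label, although it lies between the two best categories.

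The SAP states rounding where it wants it: for imputed ADHD-RS-5 items (6.6.1), Conners 3 T-scores (6.14.1.2) and missing PSI-4-SF items (6.14.2.2). For imputed CGI-I it states truncation only, so a programmer who follows the text has no instruction to round.

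What is at stake is the Week 8 proportion improved, the easily read companion to the first key secondary endpoint. Several defensible programs would give different proportions and p-values. The choice should be fixed before database lock, which is the purpose that section 1 gives for the SAP.

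**Working it through.** **The plan's own figures.** The SAP gives no figure for the CGI-I responder analysis. The 27.9% belongs to the sample size: 72 / (1 − 0.279) = 99.9, which gives the stated 100 per arm. With effect size 0.547, two-sided alpha 0.05 and 72 per arm, the t-test power is 90.3%, so the stated 90% reproduces. Neither figure bears on the point, except that 27.9% serves below as an upper limit for the share missing at Week 8.

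**Inputs.** The rule is from 6.14.2.5, the imputation from 6.14 and the scale from 5.2.1. The mean and SD of imputed CGI-I are assumptions, because the SAP gives none: mean μ of 2.5, 3.0 or 3.5 and SD σ of 1.0, 1.2 or 1.4, with normal draws clipped at 1.

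**Share of imputed draws called Improved, under three readings:**
- Exact labels: only draws clipped to 1 qualify (an unrounded draw has no chance of being exactly 2). Share = Φ((1 − μ)/σ).
- Score of 2 or less: Φ((2 − μ)/σ).
- Nearest category, that is below 2.5: Φ((2.5 − μ)/σ). This is the reference.

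| μ | σ | Exact labels | ≤2 | <2.5 |
|---|---|---|---|---|
| 2.5 | 1.0 | 6.7% | 30.9% | 50.0% |
| 2.5 | 1.4 | 14.2% | 36.0% | 50.0% |
| 3.0 | 1.2 | 4.8% | 20.2% | 33.8% |
| 3.5 | 1.0 | 0.6% | 6.7% | 15.9% |
| 3.5 | 1.4 | 3.7% | 14.2% | 23.8% |

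**Fall in an arm's responder rate** = share missing × (reference share − share under the reading). For μ = 2.5, σ = 1.0 and 10% missing, the exact-label fall is 0.10 × (50.0 − 6.7) = 4.3 points and the ≤2 fall is 0.10 × (50.0 − 30.9) = 1.9 points. Over all nine combinations:

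| Missing at Week 8 | Exact labels, points | ≤2, points |
|---|---|---|
| 5% | 0.8 to 2.2 | 0.5 to 1.0 |
| 10% | 1.5 to 4.3 | 0.9 to 1.9 |
| 27.9% | 4.3 to 12.1 | 2.6 to 5.3 |

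**Drug-placebo difference, equal missingness.** Assume means of 2.7 on drug and 3.2 on placebo, with SD 1.1. Nearest category gives 42.8% vs 26.2%, a difference of 16.6 points. With 27.9% imputed in both arms, ≤2 gives 38.2% vs 22.8% (15.4 points) and exact labels give 32.6% vs 19.5% (13.0 points). With 15% imputed the differences are 15.9 and 14.7 points.

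**Drug-placebo difference, unequal missingness.** Under the same assumptions, ≤2 costs 42.8 − 26.2 = 16.6 points per imputed drug child and 26.2 − 13.8 = 12.4 per imputed placebo child. With 5% missing on drug and 15% on placebo, the drug rate falls by 0.05 × 16.6 = 0.8 and the placebo rate by 0.15 × 12.4 = 1.9. The difference widens by about 1 point.

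**The case against.** The strongest objection is that the SAP never says only exact scores of 1 and 2 qualify. It gives labels, and a sensible programmer might apply ≤2 or round first. That is correct. A reader might infer that the plan will count imputed children as Not Improved across the board, but this follows from one literal reading, and even then draws clipped to 1 count as Improved. What stands is that the text supports no rounding, and both the exact-label and the ≤2 reading err in the same direction.

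A second objection is that the table may use observed data: it is produced for every visit, only Week 8 is imputed under 6.14, and no pooling of chi-square tests is described. This leaves real doubt. But section 6.14 covers all secondary analyses and makes no exception for 6.14.2.5, so the data source has to be stated.

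Third, 27.9% overstates the share to be imputed. It is the anticipated share of randomized subjects who do not complete, not a rate of missing Week 8 CGI-I. Early discontinuers complete the Week 8 procedures (3.3), CGI-I is scheduled at that visit (Table 1), and the visit counts as Visit 10 (6.1), so many dropouts will have an observed whole-number score. This stands, and the 5% and 10% rows are likely to be nearer the truth. Some values can still be missing, for example after loss to follow-up.

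Fourth, a reader might infer that the drug-placebo difference must shrink. The documents do not support this. It shrinks in the equal-missingness examples and widens in the unequal one.

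Finally, the analysis lies outside the multiplicity-controlled sequence in 6.14.1, where CGI-I is tested by the ANCOVA in 6.14.1.1. This stands and limits the importance of the point.

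**Conclusion.** The point holds in a limited form. Sections 6.14 and 6.14.2.5 together leave fractional imputed CGI-I scores open to misclassification, and both readings closest to the text lower the Week 8 responder rate among imputed children. The fall in an arm's rate is about 0.5 to 2.2 points at 5% missing, rising to 2.6 to 12.1 points at the 27.9% upper limit. The lower end of each range is the ≤2 reading and the upper end the exact-label reading.

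These sizes rest on normal imputed draws, the assumed means and SDs, nearest category as the reference, and imputed data being used in the Week 8 column of the table. The direction of any effect on the drug-placebo difference cannot be stated without missingness by arm. The primary analysis and the key secondary tests are unaffected.

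**What to change.** For the Week 8 categorical analysis in 6.14.2.5, impute CGI-I as an ordinal variable (declared in CLASS, with FCS LOGISTIC) so that each imputed value is a whole category from 1 to 7, then apply the existing rule. At minimum, state that an imputed value below 2.5 counts as Improved.

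Also state that the earlier visits in Table 14.2.2.5 use observed data, and how the Week 8 results are combined over the 100 imputations. The CGI-I ANCOVA in 6.14.1.1 needs no change on this account.

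The cost is a few lines of SAP text and a small change to the imputation code. The one downside is that the categorical and mean analyses of CGI-I may then use separate imputed sets, which the SAP should acknowledge. The minimum option avoids this.

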6.14.3 Exploratory Analyses**6.14.3.1** [REDACTED]

[REDACTED]
[REDACTED]
[REDACTED]

6.14.3.2 [REDACTED]

[REDACTED]
[REDACTED]

6.14.3.3 [REDACTED]

[REDACTED]
[REDACTED]

6.14.3.4 [REDACTED]

[REDACTED]
[REDACTED]

6.1.4 Supplementary Analyses

Supplementary analyses, based on the per protocol population, will be performed as in the following.

1. The primary endpoint (change from baseline in ADHD-RS-5 Total Score to Week 7 (EOS)) will be analyzed using ANCOVA model using treatment and baseline as fixed effect independent variables. This analysis will be summarized in Table 14.2.4.1.
2. The above analysis will be repeated for the Key secondary endpoints (Tables 14.2.4.2 – 14.2.4.4).

6.15 Examination of Subgroups

The primary and key secondary efficacy variables may be repeated by subgroup to explore the heterogeneity of the treatment effect across subgroups. Subgroups are defined as follows:

1. Gender (Male, Female)
2. Ages (6-9 years, 10-11 years)
3. Race (White, non-white).

This analyses will be summarized in Tables 14.2.3.1.1 to 14.2.3.1.3 for ADHD-RS-5 total score, Tables 14.2.3.2.1 to 14.2.4.2.3 for CGI-I, Tables 14.2.3.3.1 to 14.2.3.3.3 for Conners 3-PS composite T-score, and Tables 14.2.3.4.1 to 14.2.4.4.3 for WFIRS-P total score.

6.16 Pharmacokinetic (PK) Data Analysis

Plasma concentrations will be provided at the end of the study in SAS format to an external PK Scientist. This SAS data set will include subject number, visit, nominal timepoint, actual draw date, actual draw time, deviation from nominal timepoint, and concentration. Blood collection time and SM administration will be presented in Listing 16.2.13.

The Population PK model will be created separately and the analyses are not included in this SAP.

6.17 Safety Analyses

The assessment of overall safety will be based on adverse events, laboratory values, vital signs, ECGs and C-SSRS. Unless specified otherwise, comparison will be made to baseline as defined in Section 4 of the SAP.

All summary tables related to safety analyses will use the safety population. All subjects in the safety analysis set will be analyzed according to the treatment received.

6.17.1 Adverse Events

Adverse events (AEs) are described in [Section 6.4 of Protocol 812P303](#). AEs will be classified into standardized medical terminology from the Verbatim description (Investigator term) using the Medical Dictionary for Regulatory Activities (MedDRA version 20.1).

AEs will be summarized for each treatment period separately (Titration period, Maintenance period, and combined Titration and Maintenance period).

The overall incidence of AEs will be presented in Table 14.3.1.1. Subject data listing will be provided for all adverse events (Listing 16.2.7.1). Included in the listing are the reported term, PT, SOC, TEAE flag, study day when AE starts, duration, relationship, severity, action taken, outcome, and seriousness category. Data listings will be provided for subjects who experienced SAEs, have TEAEs leading to study drug discontinuation, or death (Listing 16.2.7.2, Listing 16.2.7.3, and Listing 16.2.7.4).

6.17.1.1 Treatment Emergent Adverse Events

A treatment-emergent adverse event (TEAE) is defined as an AE with a start date on or after the first dose of study drug is taken, or that worsened following first administration of study drug. TEAEs will be analyzed separately from those AEs that were not treatment-related. Only TEAE tables will be summarized. If a subject experiences more than 1 episode of a particular AE, the subject will be counted only once for that event. If a subject has more than 1 AE that codes to the same preferred term, the subject will be counted only once for that preferred term. Similarly, if a subject has more than 1 AE within a system organ class, the subject will be counted only once in that system organ class.

TEAEs will be summarized at the subject level by system organ class and preferred term for each treatment group in Table 14.3.1.2.

6.17.1.2 Severity of TEAEs

Based on the investigators determination, the severity of TEAEs will be classified as mild, moderate or severe.

If a subject experiences more than one episode of a coded TEAE, the subject will be counted only once by the maximum severity of the episode (preferred term). Similarly, if a subject has more than one TEAE within a system organ class, the subject will be counted only once by the maximum severity among TEAEs in that system organ class. TEAEs with missing severity will be considered as severe. The severity of TEAEs will be presented in Table 14.3.1.3.

6.17.1.3 Relatedness of TEAEs to SM

Based on the investigators determination, the relationship between the SM and a TEAE will be classified as not suspected (not related or unlikely related) or suspected (possibly related or definitely related). TEAE relatedness to SM will be summarized based on derived binary values as: “Drug Related” if the relationship to SM is probably or definitely related or “Not Related” if the relationship to SM is not related or unlikely related.

If a subject experiences more than one episode of a coded AE, the subject will be counted only once by the maximum relatedness of these episodes (preferred term). Similarly, if a subject has more than one AE within a system organ class, the subject will be counted only once by the maximum relatedness among AEs in that system organ class. AEs with missing relatedness will be counted as definitely related.

The summary of TEAE relatedness to SM will be presented in Table 14.3.1.4

In addition, number and percent of patients reporting common AEs ($\geq 5\%$ in any group) will be presented by PT in Table 14.3.1.5 and AEs leading to study drug discontinuation will be presented by SOC and PT in Table 14.3.1.6.

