SM	Study Medication

SOC	System Organ Class in MedDRA
TEAE	Treatment-emergent adverse event
TLF	Tables, Listings and Figures
WFIRS-P	Weiss Functional Impairment Rating Scale – Parent Version
WHODD	WHO Drug Dictionary

1 Introduction

This document describes the statistical analyses and data presentations to be performed on Study [812P303](#). This Phase III, randomized, multicenter, double-blind, 3-arm, parallel-group, and placebo controlled pivotal study of SPN-812 ER is titled “*Evaluation of SPN-812 ER 200 and 400 mg Efficacy and Safety in Children with ADHD - A Double-Blind, Placebo-Controlled, and Pivotal Trial.*”

The purpose of this statistical analysis plan (SAP) is to ensure the credibility of the study findings by specifying the statistical approaches to the analysis of the data prior to database lock. This SAP covers the planned analyses of all data collected on the eCRFs and diary pages, and will identify handling of data issues. It describes the efficacy and safety variables, anticipated data manipulations, and other details of the analyses not provided in the study protocol. The statistical analysis plan presented in this document will supersede the statistical analysis methods described in the clinical protocol. Any deviations/changes from the planned analyses described in this SAP will be identified, with justification, in the appropriate section of the clinical study report. This SAP is based on the protocol 812P303, Version 4.0, dated 17Sept2018.

2 Study Objectives

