16.17.6 C-SSRS

C-SSRS outcomes will be summarized using number and percent of subjects by categories for suicidal ideation only, suicidal behavior only and suicidality (ideation and behavior combined). The summary will be presented by treatment groups (Table 14.3.5).

Suicidal ideation and Suicidal behavior will be presented in Listings 16.2.12.1 - 16.2.12.2.

7 Validation

Supernus seeks to ensure the quality of the reports provided by ■■■ in the form of TLFs and derived datasets must pass a rigorous validation process involving the following processes.

- Derived datasets for AEs and the primary efficacy parameter must be independently reprogrammed by a second programmer based on analysis data specifications. The separate datasets produced by the 2 programmers must match 100% or in case of any differences, an explanation should be given and documented.

- Furthermore, all derived datasets will be independently programmed by BAIM institute based on analysis data specifications.
- Tables for AEs and the primary efficacy endpoint must be independently reprogrammed by a second programmer and the results from both programs must match 100% or in case of any differences, an explanation should be given and documented. Furthermore, all tables (efficacy, AEs, an all other summary tables) will be validated by BAIM institute.
- Figures must be checked for consistency against corresponding tables and listings, or independently reprogrammed if there are no corresponding tables or listings.
- Listings must be checked for consistency against corresponding tables, figures, and derived datasets.

The entire set of TLF must be checked for completeness and consistency prior to its delivery to Supernus.

The above validation process must be repeated any time TLFs are redelivered using different data. Execution of this validation process must be documented through the study in a tracking sheet which containing TFL names, name of the primary programmer, name of the QC programmer and comment. The validation tracking sheet must be submitted at each delivery of TFLs.

8 References

Abidin, R. R. (1995). Parenting Stress Index, Third Edition: Professional Manual. Odessa, FL: Psychological Assessment Resources, Inc.

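### Section 6.17.1.3 treats possibly related as suspected, but its rule for Drug Related names probably related instead, so possibly related receives neither binary value

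*SAP*

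**What the plan says.** Section 6.17.1.3 of the SAP handles relatedness in three steps.

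- **Classification.** The investigator's judgement is "classified as not suspected (not related or unlikely related) or suspected (possibly related or definitely related").
- **Derivation.** For the summary, a TEAE is *Drug Related* "if the relationship to SM is probably or definitely related or" it is *Not Related* "if the relationship to SM is not related or unlikely related". The SAP calls these derived values binary. They feed Table 14.3.1.4.
- **Missing ratings.** "AEs with missing relatedness will be counted as definitely related".

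Subjects are counted once per preferred term and once per system organ class, at their highest relatedness. No other section of the SAP defines the causality scale or says what becomes of *possibly*.

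**The concern.** The classification and the derivation are consecutive sentences and should describe the same split. Their lower halves agree: not suspected and *Not Related* both consist of not related and unlikely related. Their upper halves do not: suspected contains *possibly*, whereas *Drug Related* contains *probably*.

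A programmer who follows the derivation literally has no value to give an event rated possibly related. Such an event is one the investigator suspects, by the SAP's own definition. The missing-data rule makes the result lopsided: an unrated event is treated as definitely related and counted against the drug, while an explicit suspicion is not counted. Table 14.3.1.4 could therefore understate drug-related TEAEs in a pivotal trial in children.

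**Working it through.** The SAP gives no figure to reproduce. The check applies the derivation sentence to each possible rating.

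**Step 1. Map each level literally (all inputs from Section 6.17.1.3).**

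| Rating | On the SAP's stated scale? | SAP grouping | Derived value |
|---|---|---|---|
| Not related | yes | not suspected | Not Related |
| Unlikely related | yes | not suspected | Not Related |
| Possibly related | yes | suspected | none |
| Probably related | no | none given | Drug Related |
| Definitely related | yes | suspected | Drug Related |
| Missing | – | counted as definitely related | Drug Related |

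Of the four levels on the stated scale, 3 are mapped. Of the two suspected levels, 1 is mapped.

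**Step 2. Vary the collected code list.** The levels on the eCRF are not shown, so the second and third rows are assumptions; only the first matches the scale in the SAP. *Probably*, where collected, is counted as a suspected level.

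| Levels collected | Levels mapped | Suspected levels mapped |
|---|---|---|
| not, unlikely, possibly, definitely | 3 of 4 | 1 of 2 |
| not, unlikely, probably, definitely | 4 of 4 | 2 of 2 |
| not, unlikely, possibly, probably, definitely | 4 of 5 | 2 of 3 |

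In the first and third cases a suspected level has no value. In the second no count changes, but the classification sentence names a level that does not exist. At least one sentence is wrong in every case.

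**Step 3. Carry this through the subject-level count.** Within one preferred term or system organ class:

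- A subject whose only rating is *possibly* gets no value.
- For a subject with one *unlikely* and one *possibly* event, the result depends on the order of operations. If the maximum is taken on the original scale and then mapped, there is no value. If each event is mapped first and the maximum then taken, the subject appears as *Not Related*.
- A subject who also has a *definitely related* or unrated event is *Drug Related* either way, so not every *possibly* rating changes a count.

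**Step 4. Look for a remedy elsewhere in the SAP.**

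- The protocol may show which levels are collected. But Section 1 states: "The statistical analysis plan presented in this document will supersede the statistical analysis methods described in the clinical protocol". The derivation rule that needs correcting is the one in the SAP.
- Section 7 requires that the AE dataset "must be independently reprogrammed by a second programmer based on analysis data specifications". That may expose a blank flag, but it gives no basis in the SAP for choosing the mapping.
- Listing 16.2.7.1 includes "study day when AE starts, duration, relationship, severity, action taken, outcome, and seriousness category", so the individual ratings stay visible.
- Of Table 14.3.1.1 the SAP says only this: "The overall incidence of AEs will be presented in Table 14.3.1.1". Whether that table uses the flag cannot be told.

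**The case against.** The strongest reply is that this is a one-word slip with an evident meaning. The paragraph sets up a two-way split, repeats the lower half unchanged and calls the result binary; the natural reading is that *Drug Related* means suspected. Section 6.1 also says that specifications for the derived datasets, ADAE among them, are still to be written, and each collected code would need a value there. Section 7 adds second programming of the AE dataset and tables, with a full match or a documented explanation, and a separate institute that programs all derived datasets and validates all tables. An unmapped level would probably surface. Finally, one descriptive table is at issue, and the ratings remain in the listing.

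Much of this stands as a limit on the harm: silent loss of events is less likely than the literal rule suggests, and any misassignment could be corrected from data already collected. It does not make the text right. The SAP does not show which word is the slip, and both levels may be collected, in which case replacing a single word would leave *probably* unassigned. Later specifications would have to settle the mapping without a rule to follow, and the SAP's stated purpose is to fix the approach before database lock.

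**Conclusion.** The inconsistency is real and can be read directly from two adjacent sentences. On the SAP's own four-level scale, one of the two suspected levels has no derived value, and the derivation uses a level that is not on the scale.

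The consequence is conditional. It arises if *possibly* is a collected level, alone or together with *probably*, and the rule is programmed as written. It does not arise if *probably* is the only intermediate suspected level collected. The number of TEAEs or subjects affected cannot be derived from the document.

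The reach is narrow: Table 14.3.1.4 and any other output built on the same flag. No efficacy result or hypothesis test is affected. It should be corrected because it is a stated derivation rule for a safety table, but it does not threaten the trial's conclusions.

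**What to change.** Before database lock, compare Section 6.17.1.3 with the causality code list in the eCRF and protocol, and rewrite the two sentences to agree:

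- *Drug Related* = every suspected level: possibly and definitely related, plus probably related if it is collected.
- *Not Related* = not related or unlikely related.
- Every collected level is assigned to exactly one value. The rule for missing ratings can stay as it is.

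The cost is a check of the code list and a wording correction: one word if four levels are collected, both sentences if *possibly* and *probably* are both collected. No new data are needed and no hypothesis test changes. If *possibly* is collected, the *Drug Related* count stays the same or rises compared with the rule as written.
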